Appendix C: Listing Mockups

Listing 16.1.1	Eligibility and Treatment Assignment.....	130
Listing 16.1.2.1.1	Subject Disposition	131
Listing 16.1.2.1.2	Eligibility Not Met.....	132
Listing 16.1.2.2	Protocol Deviations.....	133
Listing 16.1.2.3	Analysis Populations.....	134
Listing 16.1.2.4	Demographics and Baseline Characteristics.....	135
Listing 16.1.2.5.1	Prior and Concomitant Medication.....	138
Listing 16.1.2.5.2	Implant and Explant Procedure.....	139
Listing 16.1.2.5.3	Stimulation Prescription (Part 1)	140
Listing 16.1.2.5.3	Stimulation Prescription (Part 2)	141
Listing 16.1.2.6.1	RA Disease Activity Assessments	142
Listing 16.1.2.6.2	ACR20 Response from Baseline on the Day of Informed Consent.....	143
Listing 16.1.2.6.2.1	ACR20 Response from Day 0.....	144
Listing 16.1.2.6.2	ACR50 Response	145
Listing 16.1.2.6.2	ACR70 Response	146
Listing 16.1.2.6.5	CDAI.....	147
Listing 16.1.2.6.6	DAS28-CRP.....	148
Listing 16.1.2.6.7	HAQ-DI	149
Listing 16.1.2.6.8	RAMRIS	150
Listing 16.1.2.6.9	EQ-5D-5L	151
Listing 16.1.2.6.10	SF-36.....	152
Listing 16.1.2.6.11	Inflammatory Biomarkers	153
Listing 16.1.2.6.12	Subject's Blinding Assessment.....	154
Listing 16.1.2.6.13	Joint Evaluator's Blinding Assessment	155
Listing 16.1.2.6.14	Co-PI Rheumatologist's Blinding Assessment	156
Listing 16.1.2.7	Adverse Events	157
Listing 16.1.2.8	Device Deficiencies	158

Listing 16.1.1
Eligibility and Treatment Assignment

Subject ID	Enrolled	Randomized	Randomization Number	Randomization Date	Treatment Assignment
xx-xxxx	Yes	Yes	xx-xx	DD-MMM-YYYY	Treatment
xx-xxxx	Yes	Yes	xx-xx	DD-MMM-YYYY	Control

SOURCE: xxxxx SAS 9.4 {program location} {run date/time}

CONFIDENTIAL

130 of 158

May not be reproduced outside of SetPoint Medical without written permission from Document Control.

Listing 16.1.2.1.1
Subject Disposition

Treatment Group	Subject ID	Consent Date	Implant Procedure Date	Randomization Date	Subject Status	Date of Exit	Reason for Withdrawal	Implant Status at Study Exit
xx-xxxx	DD-MMM-YYYY	DD-MMM-YYYY	DD-MMM-YYYY	DD-MMM-YYYY				

Programming note: This listing will include all consented subjects including screen failures, all other listings should only include all enrolled subjects.

Subject Status: Consented, Screen Failure, Enrolled, Implanted, Randomized, Withdrawn, Completed Study

Reason for withdrawal: Subject decision to withdraw consent, Investigator decision or medical judgement, Lost to follow-up, Device malfunction, Adverse event, Subject no longer eligible, Death, Study terminated, Sponsor or IRB decision, Other

SOURCE: xxxxx SAS 9.4 {program location} {run date/time}

CONFIDENTIAL

131 of 158

May not be reproduced outside of SetPoint Medical without written permission from Document Control.

Listing 16.1.2.1.2
Eligibility Not Met

Subject ID	Date of Screening Visit DD-MMM-YYYY	Inclusion		Exclusion	
		Met All?	Criteria Not Met	Met Any?	Criteria Met
xx-xxxx	DD-MMM-YYYY (-x)	Yes		Yes	xx-xxxxxxxxxxxxxxxxxxxxxxxxxxxx
xx-xxxx	DD-MMM-YYYY (-x)	No	xx -xxxxxxxxxxxxxxxxxxxx	No	
xx-xxxx	DD-MMM-YYYY (-x)	Yes		No	

SOURCE: xxxxx SAS 9.4 {program location} {run date/time}

CONFIDENTIAL

132 of 158

May not be reproduced outside of SetPoint Medical without written permission from Document Control.

Listing 16.1.2.2
Protocol Deviations

Treatment Group	Subject ID	Deviation ID	Deviation Visit	Deviation Date	Classification	Category	Reason	Associated with AE?	Associated with SAE?	Reported to IRB?	Description
Treatment	xx-xxxx										
Control	xx-xxxx										

SOURCE: xxxxx SAS 9.4 {program location} {run date/time}

CONFIDENTIAL

133 of 158

May not be reproduced outside of SetPoint Medical without written permission from Document Control.

Listing 16.1.2.3
Analysis Populations

Treatment Group	Subject ID	Population		Reason for Exclusion from PTE
		ITT [1]	PTE [2]	
Treatment	XX-XXXX	Yes	Yes	
Treatment	XX-XXXX	No	Yes	
Control	XX-XXXX	No	Yes	XXXXXXXXXXXXXXXXXXXXXXXXXXXX X

Abbreviations: ITT, intent to treat; PTE, per-treatment-evaluable; RA, rheumatoid arthritis.

[1] ITT population comprises all enrolled and randomized subjects in Stage 1 and 2

[2] PTE population comprises subjects from ITT population who have received the assigned treatment, have no major procedural protocol deviations, and for whom follow-up data are available

SOURCE: xxxxx SAS 9.4 {program location} {run date/time}

Listing 16.1.2.4
Demographics and Baseline Characteristics
(Part 1)

Treatment Group	Subject ID	Age (year)	Gender	Ethnicity	Race	RA Duration (year)	BMI (kg/m ²)	RF	ACPA	hsCRP (mg/L)	TJC28	SJC28
Treatment	xx-xxxx	xx	F	Non-Hispanic	White			Negative	Positive			
Control		xx	M	Hispanic	White			Positive	Negative			

SOURCE: xxxx SAS 9.4 {program location} {run date/time}

CONFIDENTIAL

135 of 158

May not be reproduced outside of SetPoint Medical without written permission from Document Control.

Listing 16.1.2.4
Demographics and Baseline Characteristics
(Part 2)

Treatment Group	Subject ID	CDAI Score	DAS28-CRP Score	HAQ-DI Score	Number of Prior b/tsDMARDs	Prior b/tsDMARDs	Prior Jaki (Y/N)	Ongoing Medical Condition
Treatment	xx-XXXX							
Control								

SOURCE: xxxx SAS 9.4 {program location} {run date/time}

CONFIDENTIAL

136 of 158

May not be reproduced outside of SetPoint Medical without written permission from Document Control.

Listing 16.1.2.5.1
Subjects Receiving Rescue Treatment Prior to Week 12 (ITT Population)

Subject ID	CDAI at baseline	CDAI prior to start of rescue	Type of rescue	Start date / Stop date	Rescue type ongoing in OL/LTFU (Y/N)	Rescue start relative to Day 0 (days)
XX-XXXX	Baseline: xx.x	Day 0: xx.x				

CONFIDENTIAL

137 of 158

May not be reproduced outside of SetPoint Medical without written permission from Document Control.

Listing 16.1.2.5.1
Prior and Concomitant Medication

Treatment Group	Subject ID	ATC level Preferred Term/ Medication	Start		Stop		Primary Indication	Dosage (Unit)	Route	Frequency
			Date	Study Day	Date	Study Day				
	XX-XXXX									
	XX-XXXX									

Programming Note:

1. If Ongoing is checked "Yes" list "Ongoing" under stop date column
2. Concatenate dose and unit for listing, if other unit exists then list it for units
3. Route, if Other Route is not blank, list it under "Route" column
4. Frequency, if Other Frequency is not blank, list it under "Frequency" Column

SOURCE: xxxxx SAS 9.4 {program location} {run date/time}

CONFIDENTIAL

138 of 158

May not be reproduced outside of SetPoint Medical without written permission from Document Control.

Listing 16.1.2.5.2
Implant and Explant Procedure

Treatment Group	Subject ID	Procedure Date	MicroRegulator Serial#	Procedure Start Time	Procedure Stop Time	Procedure type (Implant/Explant)	Post-Op Clearance Date
-----------------	------------	----------------	------------------------	----------------------	---------------------	----------------------------------	------------------------

XX-XXXX

XX-XXXX

SOURCE: xxxxx SAS 9.4 {program location} {run date/time}

CONFIDENTIAL

139 of 158

May not be reproduced outside of SetPoint Medical without written permission from Document Control.

Listing 16.1.2.5.3
Stimulation Prescription
(Part 1)

Treatment Group	Subject ID	Visit	Strength (uA)	Duration	Frequency	Schedule	Dose Changed at this Visit?	Dose Change Reason
-----------------	------------	-------	---------------	----------	-----------	----------	-----------------------------	--------------------

XX-XXXX

XX-XXXX

Listing 16.1.2.5.3
Stimulation Prescription
(Part 2)

Treatment Group	Subject ID	Energizer App Firmware	Energizer Bluetooth Firmware	Implant App Firmware	Implant Impedance	MicroRegulator Suspended?/ Reason
	XX-XXXX					
	XX-XXXX					

CONFIDENTIAL

141 of 158

May not be reproduced outside of SetPoint Medical without written permission from Document Control.

Listing 16.1.2.6.1
RA Disease Activity Assessments

Treatment Group	Subject ID	Visit	SJC28	TJC28	HAQ-DI Score	Subject's Pain	Subject's Global Assessment	Evaluator's Global Assessment	hsCRP (mg/mL)
Treatment	xx-XXXX	Screening Day 0 Week 4 Week 8 Week 12	xx	xx	xxx	xxx	xx	xxx	xx
Control	xx-XXXX								

SOURCE: xxxxx SAS 9.4 {program location}

CONFIDENTIAL

142 of 158

May not be reproduced outside of SetPoint Medical without written permission from Document Control.

Listing 16.1.2.6.2
ACR20 Response from Baseline on the Day of Informed Consent

Treatment Group	Subject ID	Visit	ACR20 Response	SJC28	TJC28	HAQ-DI Score	Subject's Pain	Subject's Global Assessment	Evaluator's Global Assessment	hsCRP (mg/mL)
Treatment	xx-xxxx	Day 0	N	N	N	N	N	N	N	N
		Week 4	N	N	N	N	N	N	N	N
		Week 8	Y	N	N	N	N	N	N	N
		Week 12	Y	Y	Y	N	Y	Y	N	Y
Control	xx-xxxx	Day 0	N	N	N	N	N	N	N	N
		Week 4	Y	N	N	N	N	N	N	N
		Week 8	N	N	N	N	N	N	N	N
		Week 12								

Note: Response defined by at least 20% reduction from baseline on the day of informed consent in TJC28 and SJC28 and 3 our 5 outcomes, according to ACR definition.

SOURCE: xxxxx SAS 9.4 {program location} {run date/time}

Listing 16.1.2.6.2.1
ACR20 Response from Day 0

Treatment Group	Subject ID	Visit	ACR20 Response	SJC28	TJC28	HAQ-DI Score	Subject's Pain	Subject's Global Assessment	Evaluator's Global Assessment	hsCRP (mg/mL)
Treatment	xx-xxxx	Week 4	N	N	N	N	N	N	N	N
		Week 8	Y	N	N	N	N	N	N	N
		Week 12	Y	Y	Y	N	Y	Y	N	Y
Control	xx-xxxx	Week 4	N	N	N	N	N	N	N	N
		Week 8	Y	N	N	N	N	N	N	N
		Week 12	Y	Y	Y	N	Y	Y	N	Y

Note: Response defined by at least 20% reduction from Day 0 in TJC28 and SJC28 and 3 out of 5 outcomes, according to ACR definition.

SOURCE: xxxxx SAS 9.4 {program location} {run date/time}

Listing 16.1.2.6.2
ACR50 Response

Treatment Group	Subject ID	Visit	ACR50 Response	SJC28	TJC28	HAQ-DI Score	Subject's Pain	Subject's Global Assessment	Evaluator's Global Assessment	hsCRP (mg/mL)
Treatment	xx-xxxx	Day 0	N	N	N	N	N	N	N	N
		Week 4	Y	N	N	N	N	N	N	N
		Week 8	Y	Y	Y	N	Y	Y	N	Y
		Week 12								
Control	xx-xxxx	Day 0	N	N	N	N	N	N	N	N
		Week 4	Y	N	N	N	N	N	N	N
		Week 8	N	N	N	N	N	N	N	N
		Week 12								

Note: Response defined by at least 50% reduction from baseline on the day of informed consent in TJC28 and SJC28 and 3 our 5 outcomes, according to ACR definition.

SOURCE: xxxx SAS 9.4 {program location} {run date/time}

Listing 16.1.2.6.2
ACR70 Response

Treatment Group	Subject ID	Visit	ACR70 Response	SJC28	TJC28	HAQ-DI Score	Subject's Pain	Subject's Global Assessment	Evaluator's Global Assessment	hsCRP (mg/mL)
Treatment	xx-xxxx	Day 0	N	N	N	N	N	N	N	N
		Week 4	Y	N	N	N	N	N	N	N
		Week 8	Y	Y	Y	N	Y	Y	N	Y
		Week 12								
Control	xx-xxxx	Day 0	N	N	N	N	N	N	N	N
		Week 4	Y	N	N	N	N	N	N	N
		Week 8	N	N	N	N	N	N	N	N
		Week 12								

Note: Response defined by at least 70% reduction from baseline on the day of informed consent in TJC28 and SJC28 and 3 our 5 outcomes, according to ACR definition.

SOURCE: xxxxx SAS 9.4 {program location} {run date/time}

Listing 16.1.2.6.5
CDAI

Treatment Group	Subject ID	Visit	CDAI Score	CDAI LDA (>2.8 to ≤ 10)	CDAI Remission (0 to ≤ 2.8)	CDAI MCID Response
Treatment	xx-xxxx	Screening	xx.x	--	--	--
		Day 0		--	--	--
		Week 4		No	No	No
		Week 8		Yes	No	Yes
		Week 12		Yes	Yes	Yes

SOURCE: xxxx SAS 9.4 {program location} {run date/time}

CONFIDENTIAL

147 of 158

May not be reproduced outside of SetPoint Medical without written permission from Document Control.

Listing 16.1.2.6.6
DAS28-CRP

Treatment Group	Subject ID	Visit	DAS28-CRP Score	DAS28-CRP LDA (0.6 to < 3.2)	DAS28-CRP Remission (0 to < 2.6)	DAS28-CRP MCID Response (-1.2)	DAS28-CRP Good/Moderate EULAR Response
Treatment	xx-xxxx	Screening	xx	—	--	--	--
		Day 0	xx	—	--	--	--
		Week 4	xx	No	No	No	
		Week 8	xx	Yes	No	Yes	Moderate
		Week 12	xx	Yes	Yes	Yes	Good

SOURCE: xxxxx SAS 9.4 {program location} {run date/time}

CONFIDENTIAL

148 of 158

May not be reproduced outside of SetPoint Medical without written permission from Document Control.

Listing 16.1.2.6.7
HAQ-DI

Treatment Group	Subject ID	Visit	HAQ-DI Score	HAQ-DI Response (MCID -0.22)
Treatment	xx-xxxx	Screening	xx	--
		Day 0	xx	No
		Week 4	xx	No
		Week 8	xx	Yes
		Week 12	xx	Yes

SOURCE: xxxxx SAS 9.4 {program location} {run date/time}

CONFIDENTIAL

149 of 158

May not be reproduced outside of SetPoint Medical without written permission from Document Control.

Listing 16.1.2.6.8
RAMRIS

Treatment Group	Subject ID	Visit	Synovitis score	Osteitis score	Bone erosion score	Progression? (bone erosion increase > 0.5)	CARLOS
Treatment	xx-xxxx	Screening Week 12 Change from baseline			--	No	

SOURCE: xxxxx SAS 9.4 {program location} {run date/time}

CONFIDENTIAL

150 of 158

May not be reproduced outside of SetPoint Medical without written permission from Document Control.

Listing 16.1.2.6.9
EQ-5D-5L

Treatment Group	Subject ID	Visit	Mobility	Self-Care	Usual Activities	Pain/Discomfort	Anxiety/Depression	EQ-VAS	Index value
Treatment	xx-xxxx	Screening Day 0 Week 4 Week 8 Week 12	x	x	x	x	x	xxx	xx

SOURCE: xxxxx SAS 9.4 {program location} {run date/time}

CONFIDENTIAL

151 of 158

May not be reproduced outside of SetPoint Medical without written permission from Document Control.

Listing 16.1.2.6.10
SF-36

Treatment Group	Subject ID	Visit	PCS score	MCS score
Treatment	xx-xxxx	Screening Day 0 Week 4 Week 8 Week 12		

SOURCE: xxxxx SAS 9.4 {program location} {run date/time}

CONFIDENTIAL

152 of 158

May not be reproduced outside of SetPoint Medical without written permission from Document Control.

Listing 16.1.2.6.11
Inflammatory Biomarkers

Treatment Group	Subject ID	Visit	IL-6 (pg/mL)	IL-6 % Change	SAA (μg/mL)	SAA % Change	MMP-3 (pg/mL)	MMP-3 % Change
Treatment	xx-xxxx	Screening		--		--		--
		Day 0		--		--		--
		Week 4						
		Week 8						
		Week 12						

SOURCE: xxxxx SAS 9.4 {program location} {run date/time}

CONFIDENTIAL

153 of 158

May not be reproduced outside of SetPoint Medical without written permission from Document Control.

Listing 16.1.2.6.12
Subject's Blinding Assessment

Treatment Group	Subject ID	Visit Date (Study Day)	Week 4	Why?	Week 12	Why?
XXX	XX-XXXX					

SOURCE: xxxxx SAS 9.4 {program location} {run date/time}

CONFIDENTIAL

154 of 158

May not be reproduced outside of SetPoint Medical without written permission from Document Control.

Listing 16.1.2.6.13
Joint Evaluator's Blinding Assessment

Treatment Group	Subject ID	Visit Date (Study Day)	Week 4	Why?	Week 12	Why?
XXX	XX-XXXX					

SOURCE: xxxxx SAS 9.4 {program location} {run date/time}

CONFIDENTIAL

155 of 158

May not be reproduced outside of SetPoint Medical without written permission from Document Control.

Listing 16.1.2.6.14
Co-PI Rheumatologist's Blinding Assessment

Treatment Group	Subject ID	Visit Date (Study Day)	Week 4	Why?	Week 12	Why?
XXX	XX-XXXX					

SOURCE: xxxxx SAS 9.4 {program location} {run date/time}

CONFIDENTIAL

156 of 158

May not be reproduced outside of SetPoint Medical without written permission from Document Control.

Listing 16.1.2.7
Adverse Events

Treatment Group	Subject ID	System Organ Class/ Preferred Term/ Adverse Event Verbatim	Onset Date (Day)	Resolution Date (Day)	Severity	SAE?	Relationship	Treatment/ outcome
Treatment	xx-xxxx	xxxxxx/ xxxxxx/ xxxxxx/	DD-MMM-YYYY (xx)	DD-MMM-YYYY (xx)				xxxxxx/ xxxxxx
Control	xx-xxxx	None						

Note: If a Subject has no AEs then "None" will be displayed. Adverse Events are coded in MedDRA.

Programming Note: If Ongoing is checked then list "Continuing" in the place for "Resolution Date (Day)".

SOURCE: xxxxx SAS 9.4 {program location} {run date/time}

Listing 16.1.2.8
Device Deficiencies

Treatment Group	Subject ID	Deficiency ID	Deficiency Date	Deficiency Related To	Associated with AE?	Associated with SAE?	Description
Treatment	XX-XXXX						
Control	XX-XXXX						

SOURCE: xxxxx SAS 9.4 {program location} {run date/time}

CONFIDENTIAL

158 of 158

May not be reproduced outside of SetPoint Medical without written permission from Document Control.

STATISTICAL ANALYSIS PLAN

For Long-Term Safety and Exploratory Analyses

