Device deficiency	Inadequacy of a medical device with respect to its identity, quality, durability, reliability, safety or performance. Device deficiencies include malfunctions, use errors, and inadequate labeling. [BS EN ISO 14155]

Term	Definition
Device malfunction	Failure of an investigational medical device to perform in accordance with its intended purpose when used in accordance with the instructions for use or clinical investigation protocol. [BS EN ISO 14155]
DMC	An independent data monitoring committee responsible for safeguarding the interests of study participants, assessing the safety and efficacy of the interventions during the study, and for monitoring the overall conduct of the clinical study.
EGA	A global assessment of the subject's RA activity performed by an independent, blinded Joint Evaluator using NRS from 0 (inactive) to 10 (very active).
EQ-5D-5L	
A standardized instrument for measuring general health status within the following 5 dimensions:
 
 • Mobility • Self-care • Usual activities • Pain/discomfort • Anxiety/depression 
Each dimension is scored on 5-point scale as:
 
 • No problems • Slight problems • Moderate problems • Severe problems • Extreme problems 
In addition, general health status is scored from 0 (the worst health) to 100 (the best health).

Enrolled	Subjects meeting all the inclusion and none of the exclusion criteria in whom the implant procedure is attempted.
EULAR response criteria	
A means of measuring efficacy of treatment using DAS28-CRP, incorporating both an absolute measure of disease activity, and a measure of change in activity.
 
A subject is considered having a moderate treatment response if:
 
 • DAS28-CRP score improvement from baseline to Week 12 is > 0.6 and ≤ 1.2, and the DAS28-CRP score at Week 12 is ≤ 5.1; or • DAS28-CRP score improvement from baseline to Week 12 is > 1.2, and the DAS28-CRP score at Week 12 is > 3.2. 
A subject is considered having a good treatment response if:
 
 • DAS28-CRP score improvement from baseline to Week 12 is > 1.2 and the DAS28-CRP score at Week 12 is ≤ 3.2
Flare	Worsening of RA symptoms resulting in an increase between consecutive visits in DAS28 score ≥ 1.2 , or an increase ≥ 0.6 if the first of the paired visits had DAS28 ≤ 3.2 .

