Eligibility Criteria	
Key inclusion criteria:
 
 • 22-75 years of age at informed consent • Moderate to severe RA, defined as at least 4/28 tender and 4/28 swollen joints • Demonstrated an inadequate response, loss of response, or intolerance to 1 or more biologic or targeted synthetic DMARDs, administered in accordance with their labels • Receiving treatment with at least 1 conventional synthetic DMARD for at least 12 weeks and on a continuous non-changing dose and route of administration for at least 4 weeks prior to informed consent and able to continue the same stable dose through Week 12. Missing up to 2 doses due to COVID-19 vaccination is acceptable, except during the 4 weeks preceding informed consent. 
Key exclusion criteria:
 
 • Current, regular use of nicotine-containing products. Subject does not agree to abstain from using nicotine-containing products throughout study participation. • Untreated or poorly controlled psychiatric illness or history of substance abuse • Significant immunodeficiency due to underlying illness • History of stroke or transient ischemic attack, or diagnosis of cerebrovascular fibromuscular dysplasia • Clinically significant cardiovascular disease • Neurological syndromes, including multiple sclerosis, Alzheimer's disease, or Parkinson's disease • Uncontrolled fibromyalgia • History of left or right carotid surgery • History of unilateral or bilateral vagotomy, partial or complete splenectomy • Recurrent vasovagal syncope episodes • Hypersensitivity/allergy to MRI contrast agents and/or unable to perform MRI
Primary Efficacy Endpoint	Difference between treatment and control groups in the proportion of subjects who achieve the ACR20 response at Week 12
Safety Evaluation	All adverse events reported by subjects between informed consent and Week 264 (end of study) will be tabulated.
Concomitant Medications	
 • All subjects (treatment and control) will be required to continue background therapy with at least 1 conventional synthetic DMARD started at least 12 weeks prior and at a stable dose for at least 4 weeks prior to informed consent. Dosage and type must remain stable through Week 12.

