11.2 Informed Consent and Screening

11.2.1 Informed consent

If the patient appears to be a potential candidate for the study based upon existing information, a written informed consent will be obtained. Informed consent must be obtained prior to initiation of any clinical procedures that are performed solely for the purpose of determining eligibility for research, including withdrawal from medication. Patients who have completed or are in process of washout unrelated to this study may be considered for the study. When washout is done solely in anticipation of or in preparation for the research, it is part of the research and must be done after obtaining written consent.

Clinical investigators or designees will approach the patient to obtain a written informed consent. The background of the proposed study, the implant procedure, the follow-up schedule and all potential risks and benefits will be carefully explained to each patient. The clinical investigator or designee obtaining informed consent shall:

- Avoid any coercion of or undue influence of patients to participate,
- Not waive or appear to waive patient's legal rights,
- Use language that is non-technical and understandable to the patient, and
- Provide ample time for the patient to consider participation.

Each patient must sign and date the ICF approved by an appropriate IRB during an in-office visit. The original signed ICF will be placed in the study file, and a copy will be given to the subject.

Subjects will be re-consented in situations where changes were made to the study protocol or new information about the risks, possible benefits or alternative treatments have been identified. The sponsor and IRB will notify clinical investigators in the event re-consent is necessary. In this case, subjects must sign and date the amended ICF during their next in-office visit. The original will be placed in the study file, and a copy will be given to the subject.

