15 ASSESSMENT OF SAFETY

15.1 Specifications of Safety Parameters

Adverse events (AEs) for each subject from the time the subject gives written informed consent through Week 264 (end of study) will be recorded in the EDC system and monitored. Each AE will be evaluated by clinical investigators in terms of seriousness, severity (i.e., mild, moderate, severe) and strength of relationship (i.e., not related, unlikely related, probably related, definitely related, indeterminate) to the implant device, implant procedure, explant procedure, Energizer and stimulation therapy. Each AE will be reviewed by sponsor in accordance with sponsor's SOP. The study sponsor is responsible for ensuring that all AEs are appropriately recorded, adjudicated and, when applicable, reported to the government(s), ethics committee(s) and other study centers per applicable regulations. The sponsor will also appoint an independent Data Monitoring Committee (DMC) for ongoing monitoring of subject safety (see Section 18.2.5). Subjects with RA experience a persisting set of symptoms associated with the disease and may continue to present with a wide range of symptoms during the recovery process after the implant procedure. Subjects healing appropriately may suffer from acute infections and/or inflammatory exacerbations unrelated to the procedure due to the natural course of their RA. Therefore, clinical investigators will evaluate the occurrence of AEs, excluding usual post-operative recovery signs and symptoms experienced by study subjects, unless corroborated by objective findings and/or requiring specific medical or therapeutic interventions (e.g., antibiotics).

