17.6 Analysis of Safety Measures

The incidence of AEs and SAEs from informed consent to Week 264 will be tabulated. Each AE will be coded using the Medical Dictionary for Regulatory Activities (MedDRA) and presented based on the system organ class and preferred term.

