17.8 Analysis Populations

The interim and primary efficacy analyses at Week 12 will be conducted on the intent-to-treat (ITT) population. Exploratory analyses will be performed on the ITT and per-treatment-evaluable (PTE) populations through Week 12 and on the open-label and cross-over PTE populations during the open-label, long-term follow-up. The safety will be evaluated on the safety population. All analysis populations are defined below:

- *ITT population.* All enrolled and randomized subjects in Stage 1 and 2.
- *PTE population.* Subjects from ITT population who received the assigned treatment through Week 12, have no major procedural protocol deviations (see Section 18.2.2), and for whom follow-up data through Week 12 are available.
- *Treatment to Open Label (TOL) population.* Treatment subjects from ITT population who received active stimulation through Week 12, completed Week 12 assessments, continued to receive active stimulation during open-label follow-up, and for whom follow-up data are available.
- *Control to Open Label (COL) population.* Control subjects from ITT population who received non-active (sham) stimulation through Week 12, switched to active stimulation after completing Week 12 assessments, continued to receive active stimulation during open-label follow-up, and for whom follow-up data are available.
- *Safety population.* All enrolled subjects.

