5.2 Analysis Populations

Analysis population defines the subjects to be included in an analysis. The primary efficacy analyses for the primary and key secondary endpoints will be conducted on the intent-to-treat (ITT) and per-treatment-evaluable (PTE) populations. The exploratory analyses will be conducted on the ITT population as detailed in **Table 4**. All analysis populations are defined below:

- *ITT population.* All enrolled and randomized subjects in Stage 1 and 2.
- *PTE population.* Subjects from ITT population who have received the assigned treatment, who have no major procedural protocol deviations (see Section 9.2) and for whom follow-up data are available.
- *Safety population.* All enrolled subjects in Stage 1 and 2.

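### Adverse events in consented subjects with no implant attempt reach no planned AE table or listing, although the plan promises to tabulate all AEs from informed consent

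*SAP*

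**What the plan says.** On collection and tabulation, protocol Section 15.1 states "Adverse events (AEs) for each subject from the time the subject gives written informed consent through Week 264 (end of study) will be recorded". The protocol summary (Section 4, Safety Evaluation) states "All adverse events reported by subjects between informed consent and Week 264 (end of study) will be tabulated", and Section 17.6 states "The incidence of AEs and SAEs from informed consent to Week 264 will be tabulated". Section 9.1 of the primary SAP (CLP-004) also starts the AE window at the consent date, ends it at Week 12, and promises complete listings of all AEs.

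On who is counted, protocol Section 17.8 states "The safety will be evaluated on the safety population". CLP-004 Section 5.2 defines that population as "All enrolled subjects in Stage 1 and 2", in line with the protocol. Protocol Section 3 defines an enrolled subject: "Subjects meeting all the inclusion and none of the exclusion criteria in whom the implant procedure is attempted". Consent alone is therefore not enrollment.

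On listings, the note under Listing 16.1.2.1.1 (Subject Disposition) in CLP-004 Appendix C reads "This listing will include all consented subjects including screen failures, all other listings should only include all enrolled subjects".

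**The concern.** The interval between consent and implant carries risk that the study itself imposes. Some subjects stop a biologic or targeted synthetic DMARD in order to qualify, and protocol Section 11.2.1 says of this: "When washout is done solely in anticipation of or in preparation for the research, it is part of the research". Screening also includes a gadolinium-enhanced hand MRI (Sections 11.2.2 and 12.4), whose risks Section 16.5 acknowledges. Under Section 15.4, worsening of a pre-existing condition is reportable, so a flare during washout can be an AE.

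Such events can also be the reason a subject never reaches the operating room. An infection that does not clear makes the subject a screen failure (Section 11.2.2). Contrast hypersensitivity, a positive COVID-19 test, a recent intra-articular steroid injection, and return to a biologic or targeted synthetic DMARD within the washout period each touch an exclusion criterion (31, 39, 3 and 1). If only enrolled subjects are reported, the pre-implant AEs most likely to drop out are those that stopped someone from proceeding. The plan clearly means to report pre-implant AEs, since Table 14.1.3.2 has a block for them. At stake is whether the safety report delivers what the protocol commits to, in a study whose 12-week data support a PMA application.

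**Working it through.** No sample size, power or alpha figure is involved. The check follows the definitions through to each planned output.

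1. **Window.** AE recording starts at written consent (protocol 15.1).
2. **Population.** Safety is evaluated on the safety population (17.8), which is all enrolled subjects, and enrolled means that an implant was attempted (Section 3, repeated in 10.3 and 11.3).
3. **Consequence.** A subject who consents, has an AE and then fails screening is inside the recording window but outside the safety population. A subject with a failed implant attempt is inside both.
4. **Outputs.**

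| Planned output | Subjects covered | Consented, no implant attempt |
|---|---|---|
| CLP-004 Tables 14.1.3.1 to 14.1.3.7 (AEs) | Safety population | Absent |
| CLP-004 Listing 16.1.2.7 (AEs) | Enrolled only, by the note | Absent |
| CLP-008 Tables 14.8.3.1 to 14.8.3.7 (AEs) | TOL, COL and safety population | Absent |
| CLP-008 Listing 16.8.2.8 (AEs) | TOL and COL | Absent |
| CLP-004 Table 14.1.1.1 (disposition) | All subjects | Count of screen failures |
| CLP-004 Listing 16.1.2.1.1 (disposition) | All consented | Present; an AE may appear as exit reason, without AE detail |

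The last row is a weak substitute. Protocol Section 10.4 frames the withdrawal reasons for enrolled subjects, so it is not certain that the field would be completed for a screen failure. Even if it were, the listing has no term, severity, seriousness or relationship.

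5. **Where the conflict lies.**
   - Within the protocol, Sections 4 and 17.6 promise tabulation from consent, while 17.8 restricts safety evaluation to enrolled subjects.
   - Within CLP-004, Section 9.1 promises complete AE listings, while the note confines them.
   - The note also clashes with Section 6.1, which says screen failures will appear in the data listings. Listing 16.1.2.1.2 (Eligibility Not Met) would be almost empty if restricted to enrolled subjects, because they meet all criteria by definition.

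6. **Size.** The documents give no number of consented but non-enrolled subjects and no AE rate for them, so nothing can be computed.

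**The case against.** The strongest reply is that the SAP follows the protocol's own population rule. The consent date then only marks where the window opens for enrolled subjects, and the pre-implant block of Table 14.1.3.2 fits that reading. The reading is possible, but neither document states it, and the wording of protocol Section 4 and CLP-004 Section 9.1 points the other way.

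Second, protocol Table 3 justifies the safety endpoint by events more common under treatment than control. Screen failures have no assigned group and no device exposure, so leaving them out of the comparative tables is sound. This stands, and those tables should not change.

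Third, the note sits in a mock-up and cannot have been meant literally, given Section 6.1 and Listing 16.1.2.1.2. That is a reason to correct it. Even without the note, every AE table would still omit these subjects.

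Fourth, oversight is intact. AEs are entered in the EDC, all AEs go to the DMC (protocol 15.3), the DMC sees reasons for screening failure (CLP-004 Section 4.1), and deaths and SAEs have expedited reporting (15.4). This also stands.

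Finally, some examples are weaker than they look. An infection already present at Screening is not an AE unless it worsens, and site-mandated COVID-19 screening need not be entered in the EDC (19.1). Many screen failures will have had neither washout nor contrast, because initial eligibility is checked on the day of consent and eGFR is confirmed before the MRI.

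**Conclusion.** The point holds as a gap in planned reporting: AEs and SAEs in consented subjects with no implant attempt have no place in any AE table or listing, against the stated commitments. It rests only on the definitions and on applying the programming note as written.

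Four stronger readings are tempting and are not supported:

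- A reader might infer that the SAP simply departs from the protocol. The protocol contradicts itself on the same point, and the SAP's population copies the protocol's.
- A reader might infer that these events go uncollected or unmonitored. They are recorded from consent and reviewed by the sponsor and the DMC.
- A reader might infer that the treatment-control safety comparison is biased. The omitted subjects were never randomized.
- A reader might try to size the loss by applying assumed screen-failure and AE rates to the 240 to 250 target. Neither rate is in the documents, and that target counts randomized subjects, not enrolled ones.

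Efficacy, alpha and power are untouched. This is a modest correction that should be made, because the rule drops pre-implant events selectively and the remedy is cheap.

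**What to change.** Amend the note under Listing 16.1.2.1.1 so that AE Listing 16.1.2.7, with its SAE flag, covers all consented subjects, with treatment group left blank where none was assigned. In the same edit, reconcile the note with CLP-004 Section 6.1 and Listing 16.1.2.1.2. Add one short table counting AEs and SAEs by SOC and PT in consented, non-enrolled subjects, from consent to exit. Keep the safety population for all rates and group comparisons.

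Do not ask for a breakdown by relation to washout or screening procedures. Protocol Sections 15.1 and 15.2.2 collect causality only for the implant procedure, explant procedure, implant device, Energizer and stimulation, so that breakdown would need new or retrospective classification.

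The cost is one listing filter and one small table, on data the protocol already requires in the EDC. If the sponsor prefers not to add output, the minimum is to state in the protocol and both SAPs that AE tabulation and listing are limited to enrolled subjects. That removes the contradiction but leaves these AEs unreported.
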